**4.6.2 Ribavirin**

The primary toxicity of ribavirin is hemolytic anemia. The anemia associated with ribavirin therapy may result in worsening of cardiac disease that has led to fatal and nonfatal myocardial infarctions. Patients with a history of significant or unstable cardiac disease should not be treated with ribavirin.

Significant teratogenic and embryocidal effects have been demonstrated in all animal species exposed to ribavirin. In addition, ribavirin has a multiple-dose half-life of 12 days, and so it may persist in nonplasma compartments for as long as 6 months. Therefore, ribavirin therapy is contraindicated in women, who are pregnant and in the male partners of women who are pregnant. Extreme care must be taken to avoid pregnancy during therapy and for 6 months after completion of treatment in both female patients and in female partners of male patients who are taking ribavirin therapy. At least two reliable forms of effective contraception must be utilized during treatment and during the 6-month post-treatment follow-up period. Refer to the Ribavirin Package Insert for more information.

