### **6.1.7 Pregnancy Test**

Pregnancy tests are not required for female subjects with documented prior bilateral tubal ligation, bilateral oophorectomy, or hysterectomy, or for subjects who are confirmed to be postmenopausal. Confirmation of post-menopausal status measured by follicle-stimulating hormone (FSH) will be obtained at the screening visit only for all female subjects.

For females of childbearing potential:

- A serum pregnancy test will be performed at the screening visit only and sent to the local laboratory for analysis.
- Pregnancy testing will be performed on site during the study visits as specified in Appendix A: Study Visit/ Procedures Table regardless of treatment regimen. If a urine pregnancy result is positive, a confirmatory serum human chorionic gonadotropin ( $\beta$ -hCG) test will be collected and sent to the local lab for processing.
- Subjects that receive a ribavirin-containing regimen will have pregnancy tests performed in accordance with the protocol while participating in the study. Otherwise, subjects are recommended to have monthly pregnancy test throughout the treatment period and for a minimum of 7 months after the discontinuation of ribavirin, or according to the FDA approved ribavirin label and/or standard of care.

For females of childbearing potential, and males with a female partner of child-bearing potential:

- Upon completion of the study, subjects will be counseled regarding pregnancy at their last study visit with instructions to contact their healthcare provider right away in the event that they or their female partner becomes pregnant.

For subjects with positive pregnancy test during the course of the study, refer to [Section 6.3.4](#).

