**6.1.10 Adverse Event (AE) Assessment**

Clinical outcome events that occur during the treatment period through post-treatment week 12 will be recorded and documented in the case report form as an AE or Serious Adverse Event (SAE). Refer to Section 9 Assessment of Safety for more information.

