### **6.2.3.3 Week 12 (Visit 6) - End of Treatment (EOT) Procedures**

The following assessments/procedures will be performed in-clinic:

- Pregnancy Test, Serum or Urine
- Obtain labs:
  - HCV RNA
  - CBC with differential
  - Creatinine
  - Liver panel (ALT, Alkaline Phosphatase, Total Bilirubin), AST and Direct Bilirubin
  - Additional labs as determined by the investigator
- Review concomitant medications
- Review for AEs
- Study drug accountability

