#### **6.2.4.2 Post-Treatment (PT) Week 12 (Visit 8) - End of Study/ Early Termination (ET)**

The End of Study Post-Treatment Week 12 visit will be completed at the conclusion of the post-treatment period.

Early Termination Visit should be completed when a subject discontinues or withdraws from the study during either the Treatment or Post-treatment, except when the reason for discontinuation is confirmed virologic failure ([Section 6.3.3](#)).

If a subject discontinues or withdraws from the study during the treatment period, he/she should be encouraged to complete the End of Treatment (EOT) Procedures ([Section 6.2.3.3](#)) and the Early Termination Visit ([Section 6.2.4.2](#)) within 14 days of the last study treatment dose. In the event that subject is unable to complete the visit(s) but willing to provide survival status, the study site staff should contact the subject within 14 days to collect the information.

If a subject discontinues or withdraws from the study during the post-treatment period, he/she should be encouraged to complete the Early Termination Visit ([Section 6.2.4.2](#)) except when the reason for discontinuation is confirmed virologic failure as described in [Section 6.3.3](#). If a subject is unable to complete the Early Termination visit but willing to provide survival status, the study site staff should contact the subject to collect the information.

The following assessments/procedures will be performed in-clinic, or remotely by phone with labs collected at the subject's nearest laboratory facility:

- Pregnancy Test, Serum or Urine
- Obtain labs:
  - HCV RNA
  - CBC with differential
  - Creatinine
  - Liver panel (ALT, Alkaline Phosphatase, Total Bilirubin), AST and Direct Bilirubin
  - Additional labs as determined by the investigator
- Review concomitant medications
- Review for AEs

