### **6.3.4 Pregnancy**

In the event that a positive result is obtained on a pregnancy test for a subject or a subject reports becoming pregnant during the treatment period, the administration of ribavirin (if applicable) to that subject must be discontinued immediately. The investigator is also encouraged to report the pregnancy information to the voluntary ribavirin pregnancy registry, if applicable.

Direct-acting antiviral agents may be continued at the Sponsor-investigator's discretion after discussion with the subject, if the benefit of continuing direct acting antiviral agents is felt to outweigh the potential risk. Subjects will be monitored for sustained virological response in the post-treatment period per protocol.

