#### **9.1.2 Serious Adverse Event (SAE)**

A Serious Adverse Event (SAE) is any adverse event that is any of the following:

- Fatal

- Life-threatening
- Requires initial or prolonged hospitalization
- Disability or permanent damage
- A congenital anomaly/birth defect in a neonate/infant that is suspect to exposure to a medical product prior to conception or during pregnancy
- A significant medical event determined by the investigator that may jeopardize the subject or may require medical or surgical intervention to prevent one of the outcomes listed above

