## **9.2 Methods and Timing for Capturing Safety Parameters**

The investigator is responsible for ensuring that all potential AEs (defined in [Section 9.1.1](#)) or SAEs (defined in [Section 9.1.2](#)) that occurred after subject provides written informed consent, but prior to initiation of study medication that are caused by protocol-mandated interventions will be collected and reported.

After initiation of study treatment, all AE and SAE probably related or possibly related to the study treatment or study-related procedures will be collected and reported until the end of study visit, or Early Termination.

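### Congenital anomaly is a defined SAE, but SAE collection closes about 24 weeks after Day 1, before any on-study conception can reach term, and no rule follows a pregnancy to outcome

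*Combined protocol and SAP*

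**What the plan says.** **Definition.** Section 9.1.2 lists among the SAEs "A congenital anomaly/birth defect in a neonate/infant that is suspect to exposure to a medical product prior to conception or during pregnancy".

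**Collection period.** Section 9.2 states that, once treatment has started, AEs and SAEs judged probably or possibly related "will be collected and reported until the end of study visit, or Early Termination". Section 6.1.10 agrees: "Clinical outcome events that occur during the treatment period through post-treatment week 12 will be recorded". Section 6.2.4.2 fixes the last visit: "The End of Study Post-Treatment Week 12 visit will be completed at the conclusion of the post-treatment period".

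**Risk period.** Section 4.6.2, on ribavirin: "Extreme care must be taken to avoid pregnancy during therapy and for 6 months after completion of treatment". It applies this to female patients and to the female partners of male patients.

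**Handling of pregnancy.** Section 6.1.7 refers any positive test during the study to Section 6.3.4, and Appendix A schedules tests up to Post-Treatment Week 12. Section 6.3.4 requires ribavirin to be stopped, allows the antivirals to continue at discretion, keeps monitoring virological response, and adds: "The investigator is also encouraged to report the pregnancy information to the voluntary ribavirin pregnancy registry, if applicable". At the last visit, Section 6.1.7 provides counselling, with "instructions to contact their healthcare provider right away in the event that they or their female partner becomes pregnant".

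**The concern.** The definition and the collection period do not fit together. The definition reaches back to exposure before conception, so it contemplates births many months after the last dose. The collection rule stops 12 weeks after the last dose, or sooner after Early Termination. A site that follows Section 9.2 exactly has no instruction to find, record or report a birth outcome that occurs later, even for a pregnancy it already knows about.

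What is at stake is safety capture in the ribavirin arm, which Section 8.3.1 expects to hold about 100 of the 200 subjects (presumably 80 to 120). If no congenital anomaly is reported, the absence says little, because collection normally closes before the outcome can be seen. The efficacy results are not involved.

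**Working it through.** **Inputs from the protocol**
- Treatment: 12 weeks = 84 days (Section 4.4, Table 4; Section 6.2.3.3).
- Post-treatment follow-up: 12 weeks = 84 days, counted from the last dose (Sections 6.2.4 and 6.2.4.2).
- Visit windows: ±5 days at end of treatment and at Post-Treatment Week 12 (Appendix A).
- Early Termination after stopping during treatment: within 14 days of the last dose (Section 6.2.3).
- Post-ribavirin period: 6 months in Section 4.6.2 and in the female criterion of Section 5.1; 7 months in the Protocol Summary criteria, the male criterion of Section 5.1 and Section 6.1.7.

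**Assumptions, not in the documents**
- Term is 37 to 40 weeks' gestation, that is 35 to 38 weeks (245 to 266 days) after conception.
- One month is 30.44 days.

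The plan gives no figure of its own on this point to reproduce.

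**Step 1. When collection closes, counted from Day 1**
- Nominal: 84 + 84 = 168 days = 24.0 weeks.
- Last visit 5 days late: 168 + 5 = 173 days = 24.7 weeks.
- Both windows used in full: 168 + 10 = 178 days = 25.4 weeks. This is an outer limit, because the final visit is anchored to the last dose and not to the end-of-treatment visit.
- Both windows early: 168 − 10 = 158 days = 22.6 weeks.

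**Step 2. Can a term birth fall inside?**
- Earliest on-study conception is Day 1; earliest term date is day 245.
- Smallest shortfall: 245 − 178 = 67 days = 9.6 weeks.
- Largest shortfall: 266 − 158 = 108 days = 15.4 weeks.
- Gestation at nominal closure for a Day 1 conception: 24 + 2 = 26 weeks (27.4 at the outer limit).
- Gestation at nominal closure for a conception at the last dose: 12 + 2 = 14 weeks.
- For a term birth by day 178, conception would have to precede Day 1 by at least 67 days and be missed at baseline. A conception 28 days before Day 1 would be at 28 + 2 = 30 weeks at nominal closure.

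**Step 3. Share of the post-ribavirin period after the last visit**
- 6 months: 6 × 30.44 = 182.6 days; 1 − 84/182.6 = 54%.
- 7 months: 7 × 30.44 = 213.1 days; 1 − 84/213.1 = 61%.
- Last visit 5 days late or early (89 or 79 days): 51% to 57% of 6 months, 58% to 63% of 7 months.
- Early Termination at 14 days: 1 − 14/182.6 = 92%; 1 − 14/213.1 = 93%.
- Counting the treatment weeks as exposure time too: 1 − 168/(182.6 + 84) = 37%; 1 − 168/(213.1 + 84) = 43%.

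**Step 4. Does another section close the gap?**
- Section 6.3.4 asks for no pregnancy outcome and concerns a pregnant subject, not a partner.
- Section 6.3.2 provides follow-up of AEs ongoing at drug discontinuation, but Section 9.1.1 does not name pregnancy as an AE.
- The IRB and MedWatch provisions in Sections 9.2.1 and 13.2 act on events the study has learned of. They do not create a way of learning.
- Partners appear in the exclusion criteria, the contraception rules and the ribavirin warning, but in no rule for collecting their pregnancies.

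**The case against.** A reader might infer that this SAE cannot be captured at all, or that the study would report zero anomalies whatever happened. The documents do not support that. The definition is not limited to term births. A very preterm birth, or a birth from a conception missed at baseline, could fall inside the period. The registry, MedWatch and IRB routes carry no stated end-of-study limit. This part of the objection stands, although none of these routes ensures capture.

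A reader might also infer that most post-ribavirin pregnancies go unrecorded. The 54% and 61% are shares of calendar time. Turning them into pregnancies needs an even conception rate, for which the documents give no data and which required contraception could disturb. With treatment time included, the share after study end is 37% to 43%, not a majority.

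Section 6.3.4 could be read as covering only the treatment period. Section 6.1.7 sends any positive test during the study to it, so its registry sentence reaches pregnancies detected up to Post-Treatment Week 12. That narrows the gap without supplying outcome follow-up.

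Finally, the protocol has no pregnancy-safety objective and already treats ribavirin as teratogenic, so the study is not designed to give an all-clear. The consent form, the IRB procedure and the contract are not among the documents and may say more about pregnancy. All fair, but none of this changes the cut-off written in Section 9.2.

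**Conclusion.** The conflict is real and limited in scope. The protocol defines an SAE whose usual time of occurrence lies outside its own collection period. Closure is nominally 24 weeks after Day 1, and any term birth from an on-study conception falls at least 9.6 weeks later. No section follows a known pregnancy to outcome or collects partner pregnancies, and after the last visit subjects are directed to their own provider and not to the study. In the ribavirin arm, 54% (6 months) or 61% (7 months) of the stated post-ribavirin period lies beyond the Post-Treatment Week 12 visit.

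The term-birth result rests on the 35-to-38-week assumption and holds across that range and at the latest visit date. The percentages rest only on calendar length. Few events are expected, and SVR12 and the other efficacy results are unaffected. This should be corrected because the remedy is cheap, not because it threatens the main conclusions.

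**What to change.** - **Sections 9.2 and 6.3.4:** exempt pregnancy and congenital anomaly from the end-of-study and Early Termination cut-off. Record pregnancies in subjects and, with authorization, in male subjects' partners. Follow each known pregnancy to outcome by phone or medical record. Report any congenital anomaly as an SAE whenever it becomes known. Align Section 6.1.10 with this.
- **Section 6.1.7:** ask subjects to notify the study site as well as their healthcare provider.
- **Before a collection period is set:** reconcile the Protocol Summary, Section 4.6.2, both contraception criteria in Section 5.1, and Section 6.1.7, which state both 6 and 7 months after ribavirin. Which is correct is for the sponsor to settle; the collection period should then refer to that single statement.

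**Cost:** a small amendment, a line in the consent form, partner authorization, and a few phone or record checks after Post-Treatment Week 12. Section 7.1 already allows data from the electronic medical record. No visit or test is added.

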### **9.2.1 Timing of Adverse Event (AE) Reporting**

All AEs occurring after the initiation of study treatment that are considered expected, and possibly or definitely related to the study (e.g. treatment) must be documented, and subsequently reported to the Sponsor-Investigator or designee at the end of the subject's participation in the study.

All AEs that are considered unanticipated, and possibly or definitely related to the study (e.g. treatment) must be reported to the Sponsor-Investigator or designee within 72 hours.

All unanticipated SAEs considered possibly or definitely related to the study (e.g. treatment) must be reported to the Sponsor-Investigator or designee within 24 hours of discovery.

Any AEs identified as occurring prior to the study treatment will be considered as part of the subject's medical history.

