## **9 ASSESSMENT OF SAFETY**

### **9.1 Safety Parameter and Definitions**

#### **9.1.1 Adverse Event (AE)**

An adverse event (AE) is any undesirable experience associated with the use of a medical product in a subject and includes the following:

- AE not previously observed in the subject during the protocol-specified AE reporting period, limited to signs or symptoms associated with Genotype 1 Chronic Hepatitis C and effects of study drug
- Complications that occur as a result of protocol-mandated activities
- AEs that occur prior to study treatment assignment that are related to a protocol-mandated activity
- Pre-existing medical conditions determined by investigator to have worsened in frequency or severity during the protocol-specified AE reporting period

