### **9.1.3 Clinical Laboratory Abnormalities and Other Abnormal Assessments**

Laboratory abnormalities without clinical significance are not recorded as AEs or SAEs. However, in the event that the abnormalities require medical or surgical intervention, or lead to interruption, modification or discontinuation of either of the investigational drug, they must be recorded as an AE, and if applicable as an SAE. When reporting the AE, the event should be based on the syndrome or diagnosis, and not the lab result.

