### **9.2.2 Assessment of Serious, Severity, Causality and Unexpectedness**

Investigators are required to assess all AEs occurring after the initiation of study treatment for seriousness, severity, and causality as defined below.

Serious refers to events that pose a threat to a subject's life or vital functions and is based on subject or event outcome or action criteria. An AE that does not meet any criteria for serious, as defined in [Section 9.1.2](#) should be regarded as "non-serious" AE.

Severity refers to intensity of an AE as "mild," "moderate," or "severe":

- *Mild*: Symptom(s) that do not interfere with subject's usual social and functional activities
- *Moderate*: Symptom(s) that interfere to some extent with subject's usual social and functional activities
- *Severe*: Symptom(s) that interfere significantly with subject's usual social and functional activities

Causality refers to a reasonable possibility that the AE is related to the study medication or study-related procedure. If AE is not related to study medication or study-related procedure, investigators will assess the most likely cause of AE.

Unexpected refers to whether or not the AE is described as a risk in the package insert or investigator's brochure for the study drug(s), the protocol or in the informed consent form.

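### Section 9.2.1 lets an expected related SAE wait until the subject leaves the study, and the protocol disagrees with itself on recording unrelated and pre-treatment events

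*Combined protocol and SAP*

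**What the plan says.** Section 9.2.1 (Timing of Adverse Event (AE) Reporting) sets three times for a site's report to the Sponsor-Investigator. All three are limited to events judged possibly or definitely related to the study.

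- Expected AEs "must be documented, and subsequently reported to the Sponsor-Investigator or designee at the end of the subject", which the sentence completes as the close of that person's participation.
- Unanticipated AEs have a 72-hour limit.
- For serious events: "All unanticipated SAEs considered possibly or definitely related to the study (e.g. treatment) must be reported to the Sponsor-Investigator or designee within 24 hours".

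The last sentence of the section then assigns any AE found before study treatment to the medical history.

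Other sections bear on these rules:

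- Section 9.1.2 defines an SAE as an adverse event that meets one of the listed seriousness criteria.
- Section 9.2 says that after treatment starts "all AE and SAE probably related or possibly related to the study treatment or study-related procedures will be collected and reported". Before treatment, it collects events caused by protocol interventions.
- Section 9.1.1 lists among AEs "AEs that occur prior to study treatment assignment that are related to a protocol-mandated activity".
- Section 9.2.2 has every AE after the start of treatment assessed for seriousness, severity and causality, and asks for the likeliest cause when the event is unrelated. It adds: "Unexpected refers to whether or not the AE is described as a risk in the package insert". The investigator's brochure, protocol and consent form are the other references.
- Section 6.1.10 has clinical outcome events, from the treatment period to post-treatment Week 12, entered in the case report form as AEs or SAEs. It sets no relatedness condition and refers to Section 9 for detail.
- Section 4.6.2 names hemolytic anemia as the main ribavirin toxicity and warns: "The anemia associated with ribavirin therapy may result in worsening of cardiac disease that has led to fatal and nonfatal myocardial infarctions".

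**The concern.** Speed of reporting should follow seriousness. Here it follows expectedness and relatedness first, so a serious event the protocol foresees gets the slowest route. That matters in this trial because Section 7.3 provides no DSMB, while Section 3.4 lets the sponsor stop the study on the incidence or severity of AEs. The Sponsor-Investigator can act on those grounds only with the events in hand.

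The recording rules raise a second issue. If sites cannot tell from the protocol whether an unrelated event, or one caused by a screening procedure, is to be recorded, the same event may be an AE at one center and absent at another. Section 8.2 plans safety analyses of AEs, and these inherit that variation. SVR12 is defined from HCV RNA values and does not.

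**Working it through.** **1. SAEs after the start of treatment, set against the 9.2.1 timing rules**

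| | Related | Unrelated |
|---|---|---|
| Unanticipated | 24 hours | no rule |
| Expected | end of participation | no rule |

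The expected and related cell follows because Section 9.1.2 makes an SAE an AE, and the end-of-participation sentence covers all AEs without excepting serious ones. If that sentence was meant for non-serious AEs only, the cell has no stated time. On neither reading is there an expedited route, so three of the four cells have none.

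**2. Which events count as expected**

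Section 9.2.1 uses the word unanticipated, but Section 9.2.2 defines only unexpected. If the two are the same, an event described as a risk in the package insert or protocol is expected. The ribavirin toxicity in Section 4.6.2 is described in the protocol itself, so a serious related case would fall outside the 24-hour limit.

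**3. Longest lag, if the end-of-participation rule includes SAEs**

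Inputs: 12 weeks of treatment (Table 4); post-treatment visits timed from the last dose (Section 6.2.4); a ±5 day window at post-treatment Week 12 (Appendix A).

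- Day 1 to last dose: 12 × 7 = 84 days.
- Last dose to post-treatment Week 12: 12 × 7 = 84 days.
- Lag for an event t days into treatment, in a completer: 168 − t.
- t = 0 gives 168 days (163 to 173 with the window); t = 28 gives 140; t = 84 gives 84.

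Subjects who leave early have shorter lags. Section 6.3.1 encourages an Early Termination visit within 14 days of the last treatment dose.

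**4. Number of SAEs**

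Inputs: non-cirrhotic serious AE rates in Table 2, which are 2.1% and 2.2% with ribavirin and 1.4% without; 200 subjects, with 80 to 120 per genotype group (Section 8.3.1). I take the rates as all-causality.

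- 100/100: 100 × 0.021 + 100 × 0.014 = 3.5; with 2.2%, 3.6.
- 80 (1a)/120 (1b): 80 × 0.021 + 120 × 0.014 = 3.36.
- 120 (1a)/80 (1b): 120 × 0.022 + 80 × 0.014 = 3.76.
- Chance of at least one: 1 − 0.979^80 × 0.986^120 = 0.966, up to 1 − 0.978^120 × 0.986^80 = 0.978.

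The documents do not give the share s that is both expected and related. The expected number deferred is s × (3.36 to 3.76). Assuming s = 25%, 50% or 75% gives 0.8 to 0.9, 1.7 to 1.9, or 2.5 to 2.8.

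These are means. Table 2 counts treatment-emergent events, while Section 6.1.10 records through post-treatment Week 12, so the total here would be somewhat higher.

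**5. Recording rules**

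- *Unrelated events after treatment starts.* Section 9.2 leaves them out. Section 6.1.10 sets no relatedness condition, and Section 9.2.2 instructs investigators on what to do with an AE that is unrelated. That instruction has little purpose if such events are not collected.
- *Pre-treatment events caused by the protocol.* Sections 9.1.1 and 9.2 make them AEs to collect. The last sentence of 9.2.1 makes any pre-treatment AE medical history, with no exception. Both cannot be followed for the same event.

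**The case against.** The strongest reply is that 9.2.1 is not the only channel. Section 7.2 provides monitoring visits that cover AE reporting. Under Sections 10 and 13.2 the Sponsor-Investigator is also the Principal Investigator, who must send reportable events to the IRB within its time limits, so sites would have to report those events sooner. Section 13 invokes GCP, and the second section numbered 9.2.1 adds MedWatch. The drugs are approved and used on label (Section 7.3), and Amendment 03 revised the reporting times, so tiered reporting may be deliberate.

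Part of this stands. An SAE could surface well before study exit, and the IRB procedure (SOP 502) or GCP may set limits that the documents do not show. But none of these sections states a time for a site to report to the sponsor. Monitoring takes place roughly at screening, after treatment starts and at the end, which is not a deadline. Section 7.3 explains the absence of a DSMB, not a slow route for serious events.

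A reader might infer four stronger points that the documents do not support.

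- *That 9.1.1 and 9.1.3 flatly contradict 9.2 by requiring events regardless of cause.* Section 9.1.1 counts as AEs "Pre-existing medical conditions determined by investigator to have worsened in frequency or severity during the protocol-specified AE reporting period", and 9.1.3 says of laboratory abnormalities that "lead to interruption, modification or discontinuation of either of the investigational drug, they must be recorded as an AE". Neither states a relatedness condition, but both can be read as definitions to which the 9.2 filter then applies. Section 9.1.1 also opens by tying an AE to use of a medical product. The firmer tension is between 6.1.10 and 9.2.2 on one side and 9.2 on the other.
- *That the differing causality terms in 9.2 and 9.2.1 are a further conflict.* They are loose drafting.
- *That SAEs in general stay unseen for 168 days.* That figure is the extreme: a Day 1 event, in a completer, on one of two readings.
- *That no planned analysis is touched.* SVR12 is not, but the Section 8.2 safety analyses are.

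**Conclusion.** The point holds on the text. Only SAEs that are both unanticipated and related have a 24-hour limit. An expected related SAE is deferred to study exit or, on the alternative reading, has no time at all. Unrelated SAEs have no time and fall outside the Section 9.2 collection rule, which sits poorly with Sections 6.1.10 and 9.2.2. The clash over protocol-caused pre-treatment events is direct.

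The consequences are conditional. The lag of up to about 168 days assumes that the end-of-participation rule includes SAEs. The ribavirin example also needs unanticipated to mean unexpected. About 3.4 to 3.8 SAEs of any cause are expected on treatment at the Table 2 rates, with a 97% to 98% chance of at least one; how many would be deferred depends on a share that the documents do not give. What is delayed is the sponsor's sight of the event, and nothing in these rules delays local care. This should be fixed because it concerns safety oversight in a trial without a DSMB and needs only wording. It does not threaten the primary result.

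**What to change.** 1. In 9.2.1, limit the end-of-participation rule to non-serious events and extend the section's own 24-hour limit to SAEs. For example: *Every SAE after the start of study treatment goes to the Sponsor-Investigator inside the 24-hour limit already set here, whether or not it was expected and whatever its cause.* Use one term, unanticipated or unexpected, in 9.2.1 and 9.2.2.
2. Reconcile 6.1.10, 9.2 and 9.2.2 on whether unrelated events are recorded. Step 1 requires at least unrelated SAEs to come within 9.2.
3. Except protocol-caused events from the medical-history sentence in 9.2.1.

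The cost is a protocol wording change, with no new visits or tests. Step 1 adds a few expedited reports: the average total is about 3 to 4 SAEs, some of which already have the limit, but that average is not a ceiling and follow-up to post-treatment Week 12 would raise it somewhat.

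Step 2 costs more if the choice is to record all AEs whatever their cause. At 100 per arm, Table 2 gives 82.8 + 75.0 = 157.8 to 89.0 + 75.0 = 164.0, so about 158 to 164 of 200 subjects would have at least one AE, though some of these are recorded already. That choice is the sponsor's; what is needed is a single rule that all sites can follow.
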